6.1.5 Skin Irritation Population

The skin irritation population includes all TDSs except those removed prior to the end of the 7day wear period (e.g., dropouts) for reasons unrelated to skin tolerability, or those that became detached due to lack of adhesion. TDSs that are removed due to irritation or other skin effects will be retained in the Skin Irritation Population. The Skin Irritation Population will be used for summaries of skin irritation data.

6.1.6 Adhesion Population

The Adhesion Population will be based on the TDS patches (instead of subjects). All TDSs applied will be part of the Adhesion Population except those that removed before the end of the 7-day wear period for reasons unrelated to adhesion (e.g., due to unacceptable skin irritation, because of a protocol violation, an adverse event, or subject dropout). Individual subject case reports for any subject with a TDS excluded from the Adhesion Population, and the reasons for the TDS's exclusion, will be included in the clinical study report. TDSs that became detached for reasons related to adhesion will not be excluded from the Adhesion Population. The Adhesion Population will be used for the summaries and statistics of adhesion data.

Page 9 of 61 Confidential

Demographics and baseline characteristics will be summarized for the Safety Analysis Population by treatment. Data from the PK Population will be used for PK data tables with descriptive statistics by treatment. Data from the Relative Bioavailability Population will be used for statistical comparisons between TDS 10 mg and Aricept treatments.

All protocol deviations will be assessed and documented on a case-by-case basis before the database lock, and deviations considered to have a serious impact on the efficacy results will lead to the relevant subject being excluded from the PK and Relative Bioavailability Populations. Prior to database lock, blinded adhesion data will be reviewed by the Sponsor and pharmacokinetics to identify any potential subject exclusions from the PK and Relative Bioavailability Populations.

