# **17.1.** Analysis Populations

There are 5 populations in this study:

*Randomized Population*: all subjects who signed the informed consent form and are assigned a randomization number on Day 1 of Treatment Period 1, prior to the first dose of study drug.

*Intent-to-Treat (ITT) Population*: all randomized subjects who take a least 1 dose of study drug. Demographics and baseline characteristics will be summarized for the ITT population.

*Pharmacokinetic Per-Protocol (PK-PP) Population*: all ITT subjects for a particular treatment without any major protocol deviations that could affect the pharmacokinetic endpoint for that particular treatment, who received adequate treatment to reach steady state for donepezil in the particular treatment (for example, adequate TDS wear), and who provide the plasma concentrations required to calculate the donepezil AUC0-168,SS after a particular treatment. Detailed criteria for the PK-PP Population will be listed in the SAP. Demographics and baseline characteristics will be summarized for the PK-PP Population by treatment. Data from the PK-PP Population will be used for PK data listings, with descriptive statistics, and for statistical comparison between the treatments in the Test Products and the Reference.

*Safety Population*: all randomized subjects who receive at least one dose of study drug and who have at least one safety assessment. Safety measures will be analyzed for all subjects in the Safety Population.

*Adhesion Per-Protocol (ADH-PP) Population:* The ADH-PP population will be based on the number of TDSs applied (instead of the number of subjects). All TDSs applied will be part of the ADH-PP Population except those that were intentionally removed early in the trial (e.g., because of unacceptable irritation) or from subjects who discontinued use of a TDS before the end of the 7-day wear period for reasons unrelated to adhesion (e.g., because of a protocol violation or an adverse event). Individual case reports describing any subjects/TDS who were excluded from the ADH-PP Population, and the reasons for their exclusion, will be included in the clinical study report. The ADH-PP Population will be used for the summaries and statistics of adhesion data.

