6.12 Adhesion Assessments

Page 37 of 61 Confidential

TDS observed adhesion score results (i.e., observed percent adhesion with 0% adhesion assigned to all remaining time points during the wear period in the event of complete detachment) for each TDS will be summarized by treatment as follows using the Adhesion Population:

- Summary statistics (mean, SD, minimum, Q1, median, Q3, maximum) for the mean adhesion score, where the mean adhesion score for each patch is the average of the patch adhesion scores across the entire wear period.
- Adhesion score distribution at each adhesion measurement time point post patch application (i.e., 12, 24, ..., and 168 hours).
- Average adhesion score at each adhesion measurement time point post patch application.
- Number (%) of patches that are completely detached during the 7-day wear period.
- Number (%) of patches with adhesion <50% at any adhesion measurement time point during the 7-day wear period.
- Summary of time a patch was first observed with adhesion <50% during the 7-day wear period.
- Number (%) of patches with adhesion ≥75% at all adhesion assessment time points during the 7-day wear period

In addition to the observed adhesion score, a modified adhesion score will be calculated as follows: the lowest observed adhesion score at each time point after the baseline time point (t_0) will be carried forward to subsequent time points until a lower score is observed. The modified adhesion score results for each TDS will be summarized as follows for the Adhesion Population:

- Summary statistics (mean, SD, minimum, Q1, median, Q3, maximum) for the mean adhesion score computed based on the modified adhesion scores.
- Adhesion score distribution at each adhesion measurement time point post patch application.
- Average modified adhesion score at each adhesion measurement time point post patch application.

All adhesion assessment data (observed adhesion scores as well as the modified adhesion scores as described previously) will be listed.

Within each treatment, to assess whether at least 80% of the TDS applied are at least 75% adhered throughout the 7-day wear period, a one-sided 95% confidence interval (CI) will be determined for the probability (p) that a randomly selected TDS maintains at least 75% adhesion throughout the entire wear period. If the 95% lower confidence limit exceeds 80%, then it will be concluded that at least 80% of patches are at least 75% adhered throughout the wear period.

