Let π_i denote the probability that a patch applied to the ith subject will remain at least 75% adhered during the wear period. Let y_{ij} be the response variable for the jth patch applied to the ith subject:

 $y_{ij} = \begin{cases} 1 \text{ if the TDS is at least 75\% adhered throughout the wear period} \\ 0 \text{ if the TDS is less than 75\% at some point during the wear period} \end{cases}$

The number of patches applied to the i^{th} subject with "favorable" adhesion (i.e., $y_{ij} = 1$), has a binomial distribution conditional on the random effect of subject:

 $y_i \mid s_i \sim Binomial(n_i, \pi_i)$

where n_i is the number of patches applied to the i^{th} subject. In the current study, n_i is usually 5 but can range from 1 to 5).

Since the log likelihood function of a binomial random variable with n Bernoulli trials and favorable outcome probability π is linear in the logit, $\log(\pi/(1-\pi))$, a linear model will be fit to the logit.

Using the logit link function, a conditional GLMM for the adhesion analysis is as follows:

$$\eta_i = \log\left[\frac{\pi_i}{(1-\pi_i)}\right] = \eta + s_i$$

Page 41 of 61 Confidential

where η is the intercept and s_i is the effect of the ith subject assumed to be independent, identically distributed N(0, σ_s^2).

Here s_i is a latent variable centered at 0 that quantifies an individual subject's tendency (i.e., probability) for having an applied TDS remain at least 75% adhered during the 7-day wear period in relationship to other subjects. Variation in s_i, σ_s^2 , represents variation in this propensity among subjects.

The inverse link function for this logistic model will be used to estimate π (Stroup et al 2018). From the link function, we have:

$$\hat{\pi} = \frac{1}{(1 + e^{-\hat{\eta}})}$$

with standard error estimate

 $SE[\hat{\pi}] = [\hat{\pi}(1 - \hat{\pi}) * SE(\hat{\eta})]$

and a 90% two-sided confidence interval obtained by applying the inverse of the link function to the upper and lower confidence bounds of the logistic-scale 90% two-sided confidence interval.

Page 42 of 61 Confidential

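### A patch already scored below 75% leaves the adhesion analysis if it is later removed for an unrelated reason; this matters only near the 80% limit, and a sensitivity analysis would settle it

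*SAP*

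**What the plan says.** SAP 6.1.6 starts from all patches applied and removes those taken off "removed before the end of the 7-day wear period for reasons unrelated to adhesion". The listed examples are removals "due to unacceptable skin irritation, because of a protocol violation, an adverse event, or subject dropout". Its only retention sentence reads "TDSs that became detached for reasons related to adhesion will not be excluded from the Adhesion Population". That protects a patch that came off. It does not clearly protect one that had lifted to, say, 60%, was still on the skin, and was then taken off for an adverse event.

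Protocol 17.1 (ADH-PP Population) similarly leaves out "those that were intentionally removed early in the trial (e.g., because of unacceptable irritation", and patches whose use stopped early for reasons unrelated to adhesion. In both documents the test for exclusion is the reason for removal, not the adhesion history.

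SAP 6.12 codes a patch as 0 if it is under 75% adhered "at some point during the wear period". Its decision rule is: "If the 95% lower confidence limit exceeds 80%, then it will be concluded" that at least 80% of patches meet the criterion. The main limit is Jeffreys. Clopper-Pearson and a generalized linear mixed model (GLMM) are the sensitivity analyses. Protocol 14 has adhesion scored every 12 hours and when a patch is removed at or before Early Termination, so the data to identify known failures exist.

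**The concern.** The endpoint is absorbing. Once a score below 75% is recorded the outcome is 0, and nothing later in the wear week can change it. Early removal makes an intact patch's outcome incomplete, but not that of a patch that has already failed. Discarding the second kind treats a known result as missing.

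Compared with counting such a patch as a failure, dropping it can only raise the estimate and its lower limit. The adhesion conclusion hangs on that limit. Neither planned sensitivity analysis brings these patches back, because both address the same population. SAP 6.1.5 takes more care with the parallel irritation question: patches removed because of irritation stay in the Skin Irritation Population.

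**Working it through.** **Inputs.**
- Limit (SAP 6.12): L(X, n) = 5th percentile of Beta(X + ½, n − X + ½). Pass if L > 0.80.
- Expected patches (SAP 6.12): about 270 at 5 mg/day from about 55 subjects, and about 245 at 10 mg/day from about 50 subjects, usually 5 patches each.
- Expected success rate (SAP 6.12): 0.90 to 0.95.
- Implied losses: 55 × 5 − 270 = 5 and 50 × 5 − 245 = 5.

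Patches are treated as independent throughout.

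**1. The plan's own figure.** Protocol 17.2 calls the sample size more than adequate for 80% power. The pass mark is X ≥ 207 of 245 (38 failures allowed) or X ≥ 227 of 270 (43 allowed). Exact binomial power at p = 0.90 is 0.998 and 0.999, and it reaches 80% from p of about 0.862 and 0.857. The plan's statement is confirmed.

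**2. At the expected success rate.** Restore 5 known failures to the denominator:

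| Observed | L as planned | L with 5 failures restored | Failures needed to flip |
|---|---|---|---|
| 220/245 (0.90) | 0.863 | 220/250: 0.843 | 17 |
| 233/245 (0.95) | 0.924 | 233/250: 0.902 | 33 |
| 243/270 (0.90) | 0.867 | 243/275: 0.849 | 20 |
| 256/270 (0.95) | 0.922 | 256/275: 0.902 | 36 |

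Every case still passes.

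**3. Near the boundary.**
- 206/245 gives 0.7995 (fail). Drop one known failure: 206/244 gives 0.8032 (pass).
- 204/245 gives 0.7906 (fail). Drop three: 204/242 gives 0.8016 (pass).
- 208/245 gives 0.8084 (pass). Restore three: 208/248 gives 0.7975 (fail).
- 227/270 gives 0.8015 (pass). Restore one: 227/271 gives 0.7982 (fail).

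**4. The other direction.** Intact patches are dropped as well. 207/246 gives 0.8003 (pass). Drop one intact patch: 206/245 gives 0.7995 (fail).

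**5. Probability of passing at a true p of 0.80.** Simulation, 250 patches, 40,000 runs. The removal rates, and the share of removed failing patches that had already failed when removed (half), are assumptions.

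| Early removal | Mean estimate, SAP rule | P(pass), SAP rule | P(pass), known failures kept |
|---|---|---|---|
| Unrelated to adhesion, 2% to 5% | 0.800 | 0.049 to 0.051 | 0.044 to 0.037 |
| 6% of failing, 1% of intact | 0.808 | 0.093 | 0.065 |
| 15% of failing, 2% of intact | 0.822 | 0.210 | 0.096 |

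In the first row, keeping known failures gives a mean estimate of 0.798 to 0.796, slightly low. At a true p of 0.90, P(pass) exceeds 0.996 under either rule in every scenario.

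**6. Worst case.** If all 5 lost patches were known failures, P(pass) at p = 0.80 rises from 0.045 to 0.152 (250 applied) and from 0.054 to 0.164 (275 applied).

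**The case against.** The strongest reply is that the rule is even-handed. It excludes by reason for removal, whatever the score, and the protocol calls the set per-protocol. A reader might infer that the rule discards only failures, or always pushes towards passing. The documents do not support that. Intact patches are excluded by the same sentence, step 4 shows an exclusion turning a pass into a fail, and step 5 shows no bias when removal is unrelated to adhesion. That part of the reply stands.

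It is also true that the boundary examples sit well below the expected rate, and that any pass/fail rule is sensitive near its threshold. One prior figure does lie close to that region: SAP Table 1 gives 51/60 = 0.85 for patches on the back in Study P-16012. That used an 80% adhesion cut-off, so the rate at 75% would be at least as high.

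Exclusions are also visible. SAP 6.1.6 requires case reports, SAP 6.4 counts excluded patches by reason, and SAP 6.12 lists all scores. A reader could restore the known failures by hand, but disclosure does not supply a corrected limit.

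Finally, keeping failures while dropping intact removals makes inclusion depend on outcome and biases the estimate slightly low. This is correct, and it is why the fix needs two parts.

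**Conclusion.** The gap is real but small. As written, a patch with an observed failure can leave the analysis because of a later, unrelated removal, and no planned analysis restores it. Whether this favours passing depends on whether lifting patches are removed early more often than intact ones. That is plausible, but nothing in the documents measures it, so a general claim of bias towards passing would go too far.

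At the planned success rate and about 5 lost patches per strength, the conclusion is safe. Only at an observed rate of about 0.84 to 0.85 could one to three patches decide it. These figures assume independent patches. Within-subject clustering, which the SAP handles only through its GLMM, was not modelled here. This is a cheap improvement, not a flaw that undermines the adhesion conclusion.

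**What to change.** Leave the Adhesion Population as defined and add to SAP 6.12:

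1. An analysis that keeps any patch scored below 75% before an unrelated early removal as a failure (y = 0), for the Jeffreys and Clopper-Pearson limits and the GLMM. State whether the 80% conclusion holds.
2. A Kaplan-Meier estimate, by strength, of time to first score below 75%. Patches removed early while intact are censored at removal, and the one-sided 95% lower limit at 168 hours is reported. This uses the known failures without discarding what the intact removals contributed. It assumes that an intact patch removed early would have adhered like those still worn.

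The cost is a short SAP addition and a little more analysis, and the reported adhesion rate may be slightly lower. The SAP addendum is headed as post database lock. If the lock has passed, both analyses should be labelled as added afterwards and presented as sensitivity analyses.

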6.2 Derived Data

This section describes the derivations required for statistical analysis. Unless otherwise stated, variables derived in the source data will not be re-calculated.

6.2.1 Race

Where more than one race category has been selected for a subject, these race categories will be combined into a single category labeled "Multiple Race" in the summary tables. The listings will reflect the original selected categories.

6.2.2 Baseline

For variables that will be summarized by treatment, the baseline for each period is defined as the last non-missing value (either scheduled, unscheduled or repeat) that is collected before dosing, in the relevant period.

6.2.3 Early Terminations Assessments

Early Termination (ET) from the study is defined as withdrawal during the Treatment Phase after a Donepezil TDS has been applied.

ET assessments will be summarized alongside the Follow-Up assessments as the End of Study (EoS) visit.

6.2.4 Study Day

Study day will be calculated as the number of days from first dose of study drug.

Page 10 of 61 Confidential

• date of event – date of first dose of study drug + 1

6.2.5 **Conventions for Missing and Partial Dates**

It is not expected that there will be any missing dates, however in the rare case that an AE start date or time is missing and it is unclear whether the AE is treatment emergent or not then a conservative approach will be taken and it will be assumed that the AE occurred after first dosing.

All dates presented in the individual subject listings will be as recorded on the eCRF.

6.2.6 Inexact Values

In the case where a safety laboratory variable is recorded as "> x", " \ge x", "< x" or " \le x", a value of x will be taken for analysis purposes.

6.2.7 Unscheduled Visits

Only scheduled post-baseline laboratory and vital signs values will be tabulated. Post-baseline repeat/unscheduled assessments will not be included in summary statistics. However, these repeat/unscheduled post-baseline assessments will be included in the relevant listings.

6.2.8 TDS Adhesion Assessment Scale

TDS adhesion will be assessed every 12 hours (h) after application throughout the wear period. Each time point will be assessed in person by a trained observer based on the percentage of total surface area of skin attachment.

The time of full detachment of any TDS and its 0% adherence will be recorded, and the 0% adhesion will be assigned to all remaining adhesion time points of the current wear period.

At each adhesion assessment time point, a photograph will be taken as evidence of the extent of TDS adhesion to the skin (as support of the visual observation of the adhesion percentage but not to be used for automated or photometric analysis).

Following removal of each TDS, the presence or absence of remaining adhesive residue will be recorded.

6.2.9 Skin Irritation Assessment Scale

Page 11 of 61 Confidential

Skin irritation at the patch site will be assessed prior to each TDS application and following TDS removal at 0.5, 24, 48, and 72 h. If the score is greater than 1 at 72 h post-removal, assessments will continue until a score < 1 is reported.

Application sites will be graded using the following two scales:

• an 8-point categorical Dermal Response Scale (see Table 6.2.9.1 below)

Table 6.2.9.1 Dermal Response Scale

Skin Appearance	Numeric Score
No evidence of irritation	0
Minimal erythema that is barely perceptible	1
Definite erythema that is readily visible and minimal edema	2
or minimal popular response	
What was present:	
Definite Erythema	
Minimal Edema	
Minimal Papular Response	
Erythema and Papules	3
What was present:	
• Erythema	
• Papules	
Definite Edema	4
Erythema, edema, and papules	5
What was present:	
• Erythema	
• Edema	
• Papules	
Vesicular Eruption	6
Strong reaction spreading beyond the application site	7

• a 6-point categorical Other Effects Scale (see Table 6.2.9.2 below). site will be assessed for skin irritation

Table 6.2.9.2 Other Effects Scale

Page 12 of 61 Confidential

WORLDWIDE CLINICAL TRIALS SCIENTIFICALLY MINDED · MEDICALLY DRIVEN Corium, Inc. CL-P-20003 Statistical Analysis Plan Version 2.0 Issue Date 15-JUL-2021

Observation	Score (Numeric Equivalent)		
No other effects observed	None (0)		
Slightly glazed appearance	A (0)		
Marked glazed appearance	B (1)		
Glazing with peeling and cracking	C (2)		
Glazing with fissures	F (3)		
Film of dried serous exudate covering all or part of the TDS site	G (3)		
Small petechial erosions and/or scabs	Н (3)		
What was present:			
• Small petechial erosions			
• Scabs			

Combined scores will be calculated as:

Combined Skin Irritation Score = (Dermal Response Score) + (Other Effects Score)

Only whole number scores will be used.

6.2.10 Columbia-Suicide Severity Rating Scale

The Columbia Suicide Severity Rating Scale (C-SSRS) is a brief questionnaire that provides for the identification, quantification, and standardized assessment of the occurrence and severity of suicidal ideation and behavior (see http://cssrs.columbia.edu) (Posner 2011). The "Baseline" version of the C-SSRS will be assessed at Screening. The C-SSRS "Since Last Visit" version will be assessed on all other study days [Day -1 and End of Treatment (EoT)/ET visit].

The following outcomes are C-SSRS categories and have binary responses (yes/no). The categories have been re-ordered from the actual scale to facilitate the definition of composite endpoints:

Category 1	Wish to be Dead
Category 2	Non-specific Active Suicidal Thoughts
Category 3	Active Suicidal Ideation with Any Methods (Not Plan) without Intent to Act
Category 4	Active Suicidal Ideation with Some Intent to Act, without Specific Plan
Category 5	Active Suicidal Ideation with Specific Plan and Intent

Page 13 of 61 Confidential

WORLDWIDE CLINICAL TRIALS SCIENTIFICALLY MINDED · MEDICALLY DRIVEN Corium, Inc. CL-P-20003 Statistical Analysis Plan Version 2.0 Issue Date 15-JUL-2021

Category 6	Preparatory Acts or Behavior
Category 7	Aborted Attempt
Category 8	Interrupted Attempt
Category 9	Actual Attempt (non fatal)
Category 10	Completed Suicide

Self-injurious behavior without suicidal intent is also a C-SSRS outcome which also has a binary outcome (yes/no).

Composite endpoints based on the above categories are defined below:

- Suicidal Ideation since baseline A "yes" answer at any time during treatment phase to any one of the 5 suicidal ideation questions (categories 1-5) on the C-SSRS.
- Suicidal Behavior since baseline A "yes" answer at any time during treatment phase to any one of the 5 suicidal behavior questions (categories 6-10) on the C-SSRS.

There will be no imputation of missing data for C-SSRS.

6.2.11 PK Parameters

6.2.11.1 Concentration-Time Data

Blood samples will be collected for plasma donepezil and 6-O-desmethyl donepezil (active metabolite) concentration assessments at the following timepoints (please note, "Day" refers to the day relative to Week 1 dosing in each study period):

Treatments A and B (patch applications):

- Week 1 (Days 1 to 7): Pre-TDS #1 application (Day 1), and at 2, 6, 12, 24, 48, 72, 96, 120, and 144 h after TDS #1 application.
- Week 2 (Days 8 to 14): Pre-TDS #2 application (Day 8 at 168 h after TDS #1 application, prior to removal), and at 24, 48, 72, 96, 120, and 144 h after TDS #2 application.
- Week 3 (Day 15 to 21): Pre-TDS #3 application (Day 15 at 168 h after TDS #2 application, prior to removal).
- Week 4 (Day 22 to 28): Pre-TDS #4 application (Day 22 at 168 h after TDS #3 application, prior to removal).
- Week 5 (Day 29 to 35): Pre-TDS #5 application (Day 29 at 168 h after TDS #4

Page 14 of 61 Confidential

application, prior to removal), and at 3, 6, 12, 24, 36, 48, 60, 72, 84, 96, 108, 120, 132, 144, and 156 h after TDS #5 application

• Week 6 (Day 36): Pre-TDS #5 removal (Day 36 at 168 h after TDS #5 application, prior to removal), and at 170, 174, 176, 178, and 180 h after TDS #5 removal

Treatment C (oral dosing):

- Week 1, Day 1: Pre-Dose
- Week 2: Day 8 Pre-Dose
- Week 3: Day 15 Pre-Dose
- Week 4: Day 22 Pre-Dose
- Week 5: Day 29 Pre-Dose
- Week 6: Day 35 Pre-Dose, and 1, 2, 3, 4, 6, 8, 12 and 24 h after oral administration (the 24-h sample will be collected on Day 36).

Concentration-time data prior to Week 5 will be presented by week and nominal time relative to the time of TDS application for that particular week.

For PK analysis and presentation of concentration-time data on Week 5, nominal and actual times will be expressed relative to the time of TDS # 5 application (beginning on Day 29): 0, 3, 6, 12, 24, 36, 48, 60, 72, 84, 96, 108, 120, 132, 144, 156, 168 (prior to patch removal), 170, 176, 174, 178, and 180 h.

Concentrations that are below the limit of quantification (BLQ) will be treated as zero in the data summarization and descriptive statistics. Individual plasma concentration-time data of donepezil and 6-O-desmethyl donepezil will be plotted on both linear concentration scales and on logarithmic (log10) concentration (semi-log) scales. Mean plasma concentration-time data will be presented by nominal times. For summarizing concentration and linear plots of individual time-concentration profiles, BLQ values will be set to 0. For semi-logarithmic plots of individual concentration-time profiles, BLQ values will be set to missing. Spaghetti plots (all subjects per treatment) and individual plots (comparing treatments for each subject) of the concentration-time data will be presented using actual times on both linear and semi-log scales.

The following plots will be created for donepezil and metabolite 6-O-desmethyl donepezil:

Page 15 of 61 Confidential

- 1. Mean concentration-time profiles over the entire collection period (Days 1 through 35) for Treatments A, B, and C (nominal times relative to Day 1, Week 1 dosing)
- 2. Mean concentration-time profiles for Treatments A, B, and C for Week 5 (Days 29 through 36, predose to 180 h relative to TDS #5 application; Day 35, predose to 24 h for oral dosing)
- 3. Mean trough concentration-time profiles for Treatments A, B, and C (predose on Days 1, 8, 15, 22, 29, and 36).
- 4. Spaghetti plots over the entire collection period (Days 1 through 35) for Treatments A, B, and C (actual times relative to Day 1, Week 1 dosing)
- 5. Spaghetti concentration-time profiles for Treatments A, B, and C for Week 5 (Days 29 through 35, predose to 180 h relative to TDS #5 application; Day 35, predose to 24 h for oral dosing)
- 6. Spaghetti concentration-time profiles for Treatments A, B, and C for trough concentration-time data (predose on Days 1, 8, 15, 22, 29, and 36)
- 7. Individual subject concentration-time profiles over the entire collection period (Days 1 through 35) for Treatments A, B, and C (nominal times relative to Day 1, Week 1 dosing)
- 8. Individual subject concentration-time profiles for Treatments A, B, and C for Week 5 (Days 29 through 35, predose to 180 h relative to TDS #5 application; Day 35, predose to 24 h for oral dosing)
- 9. Individual subject concentration-time profiles for Treatments A, B, and C for trough concentration-time data (predose on Days 1, 8, 15, 22, 29, and 36)

The PK population will be used to summarize concentration-time data (concentration-time summary tables, mean plots, and individual plots) and for creating concentration-time listings.

